### **9.2. Treatment Compliance**

Not applicable.

### **9.3. Adverse Events**

Throughout the course of the study (from the date of informed consent), all AEs will be monitored and recorded in source documents and on the AE eCRF. All AEs related to study treatments or procedures will be followed until resolved or stabilized based on the Investigator's clinical judgement.

AEs will be coded using MedDRA version 21.0 or higher, and presented by SOC and PT.

AEs will be defined as treatment-emergent if they start after the first treatment. AEs with missing or partial dates will be handled according to Section 6.3 with respect to assigning treatment-emergence. As a conservative approach, AEs are considered treatment-emergent unless there is clear indication that the event occurred before the first treatment in the study. In general, only TEAEs will be included in the summary tables, but all AEs will be included in the listings.

Treatment-related AEs are defined as AEs with a relationship to the study treatment of possible, probably or causal. Procedure-related AEs are defined as AEs with a relationship to the study procedure of

possible, probably or causal. Missing relatedness will not be imputed for the summarization of treatment-related or procedure-related events.

AEs increasing in severity will not be recorded as separate AEs. Missing severity will not be imputed when summarizing events by maximum severity.

At each level of summarization, summaries will include the number of subjects and the number of events. Events increasing in severity will only be counted once. For summaries by SOC and PT, a subject will be counted once at the SOC level and once at each PT within the SOC level. For summaries by SOC, PT, and maximum severity (mild, moderate, severe), a subject will be counted once at the highest severity level for which the event occurred at the SOC level and the highest severity level for each unique PT within that SOC level. Therefore, subjects will only contribute once to each PT and once to each SOC level. Summaries by SOC, PT, and maximum relationship (not related, unlikely, possible, probable, causal relationship) will be handled similarly to the summaries by maximum severity. Summaries presenting frequency of AEs by SOC and PT will be ordered by overall descending frequency of SOC and then, within a SOC, by overall descending frequency of PT.

The following tables will be produced:

- An overall summary of the number and percentage of subjects reporting TEAEs, treatment-related TEAEs, procedure-related TEAEs, serious TEAEs, serious treatment-related TEAEs, serious procedure-related TEAEs, and TEAEs leading to study discontinuation.
- TEAEs overall and by SOC and PT
- Study-treatment-related TEAEs overall and by SOC and PT
- Study-procedure-related TEAEs overall and by SOC and PT
- Serious TEAEs, overall and by SOC and PT
- Serious Study-treatment-related TEAEs, overall and by SOC and PT
- Serious Study-procedure-related TEAEs, overall and by SOC and PT
- TEAEs by maximum severity, overall and by SOC and PT
- TEAEs by maximum relationship to study treatment, overall and by SOC and PT
- TEAEs by maximum relationship to study procedure, overall and by SOC and PT
- TEAEs leading to study discontinuation, overall and by SOC and PT

All TEAEs and Non-TEAEs will be listed, sorting by subject number, onset date, and end date (placing missing and partial dates first), then alphabetically by SOC and PT within SOC. Serious TEAEs, treatment-related TEAEs, procedure-related TEAEs, and TEAEs leading to study discontinuation will also be listed separately.

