### 9.1 DEFINITIONS

#### 9.1.1 Adverse Events (AE)

The reference safety data will be the current VOLIFT with Lidocaine instructions for use.

According to EN ISO 14155:2011 an AE is any untoward medical occurrence, unintended disease or injury, or untoward clinical signs (including abnormal laboratory findings) in subjects, users or other persons, whether or not related to the investigational medical device or the comparator device.

NOTE 1: This definition includes events related to the investigational medical device or the comparator.

NOTE 2: This definition includes events related to the procedures involved.

NOTE 3: For users or other persons, this definition is restricted to events related to investigational medical devices.

Adverse events are collected once informed consent has been obtained, regardless of whether or not the subject has been administered study treatment. Disease signs and symptoms that existed prior to the study treatment are not considered AEs unless the condition recurs after the subject has recovered from the pre-existing condition or the condition worsens in intensity or frequency during the study.

All AEs ongoing at the exit visit must be followed until resolved or stable, based on the investigator's clinical judgment.

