### 9.2.2 Severity

The Investigator will determine the severity classification based on the following definitions, his/her experience in the use of dermal fillers and/or the subject’s description of the event. ISR severity is defined on the ISR 30-Day Diary.

The term “severe” is used to describe the intensity of an AE; the event itself could be of relatively minor clinical significance (e.g., ‘severe’ headache). This is not the same as “serious”. Seriousness of AEs is defined in *Section 9.1.2: Serious Adverse Events (SAE)*.

Severity will be assessed as:

- **Mild**            The AE does not interfere in a significant manner with the subject’s normal functioning level. It may be an annoyance.
- **Moderate**      The AE produces some impairment of function but not hazardous to health. It is uncomfortable and/or an embarrassment.
- **Severe**            The AE process significant impairment of functioning or incapacitation and/or it is a hazard to the subject.

If an AE changes in severity, the worst severity should be reported.

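### The treatment-emergent AE definition rests on start date alone, so an AE recorded before injection that worsens afterwards is left out of the AE summary tables

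*SAP*

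**What the plan says.** Four rules in the two documents act together.

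- **When collection starts.** Protocol 9.1.1: "Adverse events are collected once informed consent has been obtained, regardless of whether or not the subject has been administered study treatment". SAP 9.3 and Protocol Table 9.1 agree. Protocol 6.1.3 and SAP 3.8.1 give a 14-day screening period, which washout can extend, so AEs can be recorded before any injection.
- **What counts as treatment-emergent.** SAP 9.3: "AEs will be defined as treatment-emergent if they start after the first treatment". A default follows: "AEs are considered treatment-emergent unless there is clear indication that the event occurred before the first treatment in the study".
- **How worsening is recorded.** SAP 9.3: "AEs increasing in severity will not be recorded as separate AEs", and for counting, "Events increasing in severity will only be counted once". Protocol 9.2.2 adds: "If an AE changes in severity, the worst severity should be reported".
- **What is tabulated.** SAP 9.3: "In general, only TEAEs will be included in the summary tables, but all AEs will be included in the listings".

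Protocol 9.1.1 also deals with signs and symptoms that were present before study treatment. They are not AEs "unless the condition recurs after the subject has recovered from the pre-existing condition or the condition worsens in intensity or frequency during the study". The protocol does not define treatment-emergent and does not say which date is the onset when a sign becomes an AE by worsening.

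**The concern.** Worsening after exposure is one of the things a treatment-emergent summary exists to show, and Protocol 9.1.1 recognises worsening as a reason to call a pre-existing sign an AE. The SAP definition has no counterpart. Take an AE recorded as mild during screening that becomes severe after the injection. It is one record, with a pre-injection start date and a severe grade, and by rule it is not treatment-emergent.

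At stake is the completeness of the AE summary tables in a single-arm study of 60 treated subjects, where a single event is visible in a percentage. The omission runs one way: it can lower the reported TEAE frequency or the maximum severity, and it cannot raise them. A second problem is consistency. Because the onset date of a worsening is not defined, two sites could enter the same clinical course differently, one as a pre-treatment AE and the other as a new post-treatment AE.

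**Working it through.** The point rests on a definition, so there is no stated figure to reproduce. The check applies the SAP 6.3 date rules and the SAP 9.3 definition to test cases, then looks through the table index for any output that would pick the event up.

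**Step 1. Classification.** By SAP 6.2 a subject is enrolled once treated, so the enrolment date used for imputation is the injection date. Every case is an AE already recorded before injection that worsens afterwards, except the last.

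| Start date on the record | Date used | Result |
|---|---|---|
| Complete, 5 days before injection | As recorded | Not a TEAE |
| Day missing, same month as enrolment | Injection date | TEAE through the default |
| Whole date missing | Injection date | TEAE through the default |
| Day missing, earlier month than enrolment | First of that month | Not a TEAE |
| Worsening entered as a new AE, 2 days after injection | As recorded | TEAE, but SAP 9.3 rules out a separate record when a recorded AE increases in severity |

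The default and the imputation rules help only some records with incomplete dates. A complete pre-injection date is itself the indication that switches the default off.

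**Step 2. Where the event appears.** From SAP 9.3 and the indexes in SAP 15 and 17:

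- AE Tables 14.3.1.1 to 14.3.1.11: all 11 are limited to TEAEs, so the event is in 0 of 11.
- Listings 14.3.2.1 to 14.3.2.4 (serious, treatment-related, procedure-related, leading to discontinuation): all limited to TEAEs, so it is absent.
- Table 14.3.4.4 (volume by AE presence): its title in the index is restricted to TEAEs. A subject whose only AE is of this kind falls in the absent group.
- Listing 16.2.7.2 (non-treatment-emergent AEs, Screened Set): present.
- Section 14.3.3 (narratives), Table 14.1.1 and Listing 16.2.1 (disposition): not limited to TEAEs, so a serious event or a discontinuation could appear there.

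**Step 3. What the single record can show.** With only the worst grade on the record, the analyst cannot tell whether that grade was reached before or after the injection. Rewording the TEAE definition without capturing a date of worsening would therefore not be programmable.

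**Step 4. Size.** One affected subject with no other TEAE changes the overall TEAE rate by 1/60 = 1.7 percentage points; two change it by 2/60 = 3.3. The documents give no rate of AEs in screening and no rate of worsening. Purely as an assumption: if 5% to 10% of subjects had an AE ongoing at injection (0.05 × 60 = 3 to 0.10 × 60 = 6) and one third of these worsened, 1 to 2 subjects would be affected. Nothing in the documents supports either input.

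**The case against.** Four objections deserve an answer.

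**The event is not hidden.** A reader might infer that a post-injection worsening, even one that is serious or ends participation, would be visible only in the non-TEAE listing. The documents do not support that. SAP 7.1 tabulates reasons for discontinuation for the Screened Set, the 14.3.3 narrative section is not restricted to TEAEs, and Protocol Table 9.1 and Section 9.3 require expedited reporting of serious events from consent onward. This objection stands. What is lost is the count in the AE summary tables and TEAE listings.

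**Protocol 9.1.1 may already solve it.** A reader might infer that the two documents flatly contradict each other, with handling that turns on whether the sign began before or after consent. The protocol sentence turns on study treatment, not consent. On one reading, a sign that appears in screening first becomes an AE when it worsens, has a post-injection onset, and is a TEAE. The same section also collects AEs from consent, so the other reading is equally open. The objection narrows the point to AEs already recorded before injection, and the ambiguity is itself a reason to settle the onset date.

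**The case is rare.** Screening is nominally 14 days. Eligibility is confirmed before treatment, and the exclusions remove active problems in the mouth area and uncontrolled disease. Expected local reactions go into a diary that starts on the treatment day. This stands. A reader might also infer that the missed event would be the study's only serious or severe one; that is possible, but nothing in the documents makes it likely.

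**A new record for worsening conflicts with Protocol 9.2.2.** That is correct, and the fix has to deal with it.

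The table shells are redacted and the eCRF completion instructions are not among the documents, so onset dating may be addressed there. The SAP text should still carry the rule.

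**Conclusion.** The gap is real and limited. Under SAP 9.3 as written, an AE recorded between consent and first injection, with a complete pre-injection onset date, that worsens after the injection is non-treatment-emergent and is missing from every AE summary table. The phrase allowing exceptions to TEAE-only tables gives nominal room, but no planned AE table uses it.

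This conclusion assumes that the site recorded the sign as an AE before injection and that the indexes describe the tables as they will be programmed. It does not show that any event will be missed. The effect is 1.7 percentage points per affected subject, the number of such subjects is unknown and probably small, and the primary endpoint is untouched. The change is worth making because the rule can err only toward understating harm after treatment and is cheap to repair.

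**What to change.** **SAP 9.3.** Define a TEAE as an AE that starts on or after first treatment, or that was present before first treatment and, on or after it, worsens in severity or frequency or becomes serious.

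**Data capture, only for AEs ongoing at first injection.** Record when the worsening occurred, in one of two ways: add the severity at first injection and a worsening date to the existing record, or open a new record dated at the worsening. Keep the single-record rule for all other AEs.

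**Reconcile the text.** Whichever route is taken, amend the sentence in SAP 9.3 that bars separate records and check it against the worst-severity rule in Protocol 9.2.2. State which date is the onset when a sign present before treatment becomes an AE by worsening under Protocol 9.1.1.

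**If data are already collected.** SAP 11 refers to an item that the database did not collect, which suggests the database was already built. In that case, query only the few AEs ongoing at injection for a worsening date and the severity at injection.

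**Cost.** A SAP sentence with its reconciling edits, a short eCRF instruction or a handful of queries, minor programming, and possibly a slightly higher TEAE count. Adding the two fields to the existing record leaves the worst-severity rule intact; a new record needs more reconciliation and, late in the study, some re-entry.

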### 9.2.3 Causality

Relationship to a device refers to a determination of the relationship (if any) between an AE and the device. A causal relationship is present if a determination is made that there is a reasonable possibility that the AE may have been caused by the device.

An AE could be considered procedure-related when, in the judgment of the Investigator, it is reasonable to believe that the event is associated with the procedure, regardless of the relationship to the study device. Procedure-related causes that contribute to the occurrence of the event can be attributed to other products, surgical techniques, or medications required specifically for the procedure.

Relationship to the device or procedure must be determined by the Investigator and cannot be delegated to other study staff.

Causality will be assessed as:

**01 Not related:** relationship to the device or procedures can be excluded when:

Clinical Study Protocol: CMO-MA-FAS-0512

---

- the event is not a known side effect of the product category the device belongs to or of similar devices and procedures;
- the event has no temporal relationship with the use of the investigational device or the procedures.
- the serious event does not follow a known response pattern to the medical device (if the response pattern is previously known) and is biologically implausible;
- the discontinuation of medical device application or the reduction of the level of activation/exposure - when clinically feasible – and reintroduction of its use (or increase of the level of activation/exposure), do not impact on the serious event;
- the event involves a body-site or an organ not expected to be affected by the device or procedure;
- the serious event can be attributed to another cause (e.g. an underlying or concurrent illness/ clinical condition, an effect of another device, drug, treatment or other risk factors);
- the event does not depend on a false result given by the investigational device used for diagnosis, when applicable;
- harms to the subject are not clearly due to use error;
- in order to establish the non-relatedness, not all the criteria listed above might be met at the same time, depending on the type of device/procedures and the serious event.

**02 Unlikely:** the relationship with the use of the device seems not relevant and/or the event can be reasonably explained by another cause, but additional information may be obtained.

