**03 Possible:** the relationship with the use of the investigational device is weak but cannot be ruled out completely. Alternative causes are also possible (e.g. an underlying or concurrent illness/ clinical condition or/and an effect of another device, drug or treatment). Cases where relatedness cannot be assessed or no information has been obtained should also be classified as possible.

**04 Probable:** the relationship with the use of the investigational device seems relevant and/or the event cannot reasonably be explained by another cause, but additional information may be obtained.

**05 Causal relationship:** the serious event is associated with the investigational device or with procedures beyond reasonable doubt when:

- the event is a known side effect of the product category the device belongs to or of similar devices and procedures;
- the event has a temporal relationship with investigational device use/application or procedures;
- the event involves a body-site or organ that the investigational device or procedures are applied to;
- the investigational device or procedures have an effect on;

Clinical Study Protocol: CMO-MA-FAS-0512

---

- the serious event follows a known response pattern to the medical device (if the response pattern is previously known);
- the discontinuation of medical device application (or reduction of the level of activation/exposure) and reintroduction of its use (or increase of the level of activation/exposure), impact on the serious event (when clinically feasible);
- other possible causes (e.g. an underlying or concurrent illness/ clinical condition or/and an effect of another device, drug or treatment) have been adequately ruled out;
- harm to the subject is due to error in use;
- the event depends on a false result given by the investigational device used for diagnosis, when applicable;
- in order to establish the relatedness, not all the criteria listed above might be met at the same time, depending on the type of device/procedures and the serious event.

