## **11. Changes from Analysis Planned in Protocol**

Subject study product compliance was to be summarized using descriptive statistics, but this information was not collected in the database.

This document is [REDACTED]

[figure not shown]

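### An adverse event whose device-relationship field is blank at a data cut drops out of the treatment-related summaries, although the protocol's default for absent information is 'possible', which the SAP counts as related

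*SAP*

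**What the plan says.** Protocol 9.2.3 (Causality) sets a five-grade scale from *not related* to *causal relationship*. Under grade 03, *possible*, it gives a default for absent information: "Cases where relatedness cannot be assessed or no information has been obtained should also be classified as possible". The grading belongs to one person: "Relationship to the device or procedure must be determined by the Investigator and cannot be delegated to other study staff".

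SAP 9.3 (Adverse Events) draws the line between related and unrelated at that grade: "Treatment-related AEs are defined as AEs with a relationship to the study treatment of possible, probably or causal". Procedure-related events are defined in the same way. On blank fields it says: "Missing relatedness will not be imputed for the summarization of treatment-related or procedure-related events". For the tables by strongest relationship it says: "Summaries by SOC, PT, and maximum relationship (not related, unlikely, possible, probable, causal relationship) will be handled similarly to the summaries by maximum severity". That list has five grades and no row for missing.

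The same section treats uncertain onset differently: "As a conservative approach, AEs are considered treatment-emergent unless there is clear indication that the event occurred before the first treatment in the study". On where events appear, it says: "In general, only TEAEs will be included in the summary tables, but all AEs will be included in the listings".

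**The concern.** The protocol and the SAP each have a rule for an event with no causality information, and the two lead to different outcomes. Under the protocol default the event is *possible* and hence related. Under the SAP a blank field meets none of the three qualifying grades, so the event is not counted as related.

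The outputs affected on the device side are the treatment-related rows of the overall summary (Table 14.3.1.1), the treatment-related table (14.3.1.3), the serious treatment-related table (14.3.1.6), the table by maximum relationship to treatment (14.3.1.9) and the listing of treatment-related TEAEs (14.3.2.2). The study is single-arm, so there is no comparator event rate, and attribution to the product rests on the Investigator's causality grade. Injection site reaction diary entries are planned as a listing only (SAP 9.5). A rule that can lower the related counts and never raise them therefore deserves attention even if it seldom operates.

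SAP section 10 also has all tables and listings produced at the 6-month interim from whatever data are then available. It is a reasonable inference, though not something the documents state, that blanks are more likely then than at final lock.

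**Working it through.** The plan states no figure on this point, so there is nothing to reproduce. The check is a comparison of rules, followed by simple arithmetic on the planned denominator.

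**Step 1. Follow one treatment-emergent event with no device-relationship information.**

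| | Protocol default applied | SAP rule applied to a blank |
|---|---|---|
| Grade carried into analysis | possible | none |
| Meets the SAP 9.3 definition of treatment-related? | yes | no |
| Counted in 14.3.1.3 (and 14.3.1.6 if serious) | yes | no |
| Named category in 14.3.1.9 | possible | none named in the text |
| In the related-TEAE listing 14.3.2.2 | yes | no |
| In the overall TEAE tables and all-AE listings | yes | yes |

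**Step 2. Direction.** Counting a blank as *possible* can only add to the related count; leaving it out can only subtract. SAP 9.3 reports events as well as subjects, so each blank removes one from the related event count. It removes a subject only if that subject has no other TEAE graded possible, probable or causal.

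**Step 3. Size.** Input: 60 treated subjects (SAP 3.4), which is the planned Safety Analysis Set because that set consists of all enrolled, treated subjects (SAP 5.2, 5.3 and 6.2). Let k be the number of subjects whose only potentially related TEAE has a blank field. The documents do not give k, so the range is an assumption.

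Shortfall = k/60:

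- k = 0: 0
- k = 1: 1/60 = 1.7 points
- k = 2: 2/60 = 3.3 points
- k = 3: 3/60 = 5.0 points
- k = 6: 6/60 = 10.0 points

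**Step 4. An assumed example for scale.** Suppose 3 subjects have a TEAE recorded as related and 3 more have only a blank one. The exact 95% interval for x out of n has as its lower limit the 0.025 quantile of Beta(x, n − x + 1), and as its upper limit the 0.975 quantile of Beta(x + 1, n − x).

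- SAP rule: 3/60 = 5.0% (1.0% to 13.9%)
- Protocol default: 6/60 = 10.0% (3.8% to 20.5%)

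If no event were recorded as related, one blank would be the difference between 0/60 = 0% and 1/60 = 1.7%. Summaries are also presented by gender (SAP 6.1). The denominator there is smaller than 60 if both genders are enrolled, so the shift per subject is larger, but the documents give no planned split.

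**The case against.** The strongest reply is that the two rules act at different steps. The protocol default is an instruction to the Investigator at data entry. An Investigator who follows it enters *possible*, and the SAP counts that as related. What remains for the SAP rule is a field nobody completed, and the proper remedy for that is a query, not a programmed grade standing in for a judgement reserved to the Investigator. The protocol also has safeguards against blanks: AE entries are reviewed by the Clinical Monitor and serious events are reported within 24 hours (Table 9.1), serious events are followed up (9.3), and the Investigator attests that the eCRFs are complete (11.10). This stands, and it limits how often the rule bites. It does not remove the difference, because the SAP provides for blanks and its provision gives the opposite result from the protocol default.

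Three stronger readings are tempting, and the documents do not support them.

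- *That the SAP departs from the protocol without declaring it.* SAP section 11 lists only one change: "Subject study product compliance was to be summarized using descriptive statistics, but this information was not collected in the database". But Protocol 10.5.3 leaves the missing-data strategy to the SAP, and Protocol 10.5.4 plans summaries by relationship with no rule for missing values. The SAP can fairly be read as filling a gap it was given to fill.
- *That the protocol requires blank procedure relatedness to count as possible.* The wording of *possible* refers to the device only. Extension to the procedure is implied by the shared scale, not written.
- *That events are hidden.* They remain in the overall, SOC/PT and serious TEAE tables and in the listings. The table shells are redacted, so a missing row in the maximum-relationship tables may exist.

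The contrast with the conservative onset rule is also only supporting evidence: SAP 9.3 leaves missing severity unimputed as well.

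**Conclusion.** The point holds for device relatedness. For a relationship field still blank at a data cut, SAP 9.3 gives a different result from the default in Protocol 9.2.3, and always in the direction of fewer treatment-related events. The size is 1.7 percentage points per affected subject out of 60, and nothing if every field is complete. This assumes that 60 subjects are treated as planned, and that an affected subject has no other event recorded as related. The number of blanks is unknown.

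A reader might infer that related toxicity will be under-reported. The documents support only that it can be, and only in the relatedness outputs. The study is descriptive and no decision rule uses the related-event rate, so this is a modest inconsistency that is worth removing because removal is cheap.

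**What to change.** In SAP 9.3, replace the sentence on missing relatedness with a rule in three parts:

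1. Blank relationship fields are queried to the Investigator before each data cut, interim and final.
2. Any device relationship still missing is counted as *possible* in the treatment-relatedness summaries (Tables 14.3.1.1, 14.3.1.3, 14.3.1.6 and 14.3.1.9), consistent with Protocol 9.2.3. The listings show the field as missing, so the recorded data stay visible.
3. The same handling applies to procedure relatedness (Tables 14.3.1.4, 14.3.1.7 and 14.3.1.10, and the procedure rows of 14.3.1.1). It is described as a conservative SAP convention on the shared scale and not as an explicit protocol requirement.

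The separate listings of treatment-related and procedure-related TEAEs (14.3.2.2 and 14.3.2.3) should select events by the same rule.

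The cost is a short SAP edit, a simple derivation step and a query run before each cut. Related-event rates may come out slightly less favourable. An event with both fields blank would count as both treatment-related and procedure-related, which a footnote giving the number of such events would make plain.
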